Radiologic assessment will occur at screening and the end of cycles 6, 12, and 24 (if applicable). Radiologic assessment at other time points will be at the discretion of the treatment team. PROs Measurements and CBA will begin at screening and will occur at the end of every 6 cycles throughout the duration of the study and extension period. If there are any signs of worsening prior to study evaluations, then the Principal Investigator (PI) should complete earlier assessment for evaluation of response.

Therapy will be discontinued if there is evidence of worsening disease or drug related dose-modifying toxicity that requires removal from therapy. Treatment may otherwise continue to the end of the study intervention phase and subsequent extension period provided the subject meets the criteria for starting subsequent cycles and does not meet criteria for removal.

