8.2.2 Assessment of Patient Reported Outcome Measures (PROMs)

Quality of life is an essential component of high-quality clinical care.⁵³ The Patient Reported Outcomes Measurement Information System (PROMIS) is a validated parent/patient-reported scoring system that was developed with the National Institutes of Health (NIH) that can compare values across a variety of medical conditions.^{33,34} PROMIS is validated in individuals aged 8 years and older.⁵⁶⁻⁵⁸ A caregiver proxy report for the PROMIS measure is also available for use in children; for individuals younger than 8 years old, assessments must be completed by a caregiver proxy. PROMIS is considered to be the gold standard for HRQOL measurement in clinical trials. The recall timeframe for each question includes the past week.

Each question has five response categories. A raw score can be calculated for each PROMIS subscale. Raw scores are then translated into a T-score metric with mean of 50 (standard deviation of 10). A higher PROMIS T-score represents more of the concept being measured. Additional details for scoring and measure interpretation are available at <https://www.healthmeasures.net/score-and-interpret/interpret-scores/promis>. Higher scores represent better functioning. A difference or change in score of three points on the PROMIS Pediatric scale is considered a minimally important difference (MID).

In consultation with subjects, patient advocates, clinicians, and psychometricians, we will use global health measures as the **primary outcome** and pain interference as the **secondary outcome**. For exploratory outcomes, we will administer PROMIS measures for fatigue, anxiety, and depression. This survey battery will be administered every 6 cycles, starting at enrollment and continuing during participation in the study.

For subjects **18+ years old at enrollment**, please refer to “Adult subject 18+ y/o” column in [Table 8-3](#). In total, this battery of measures will include **26 items**. We will also include 2 open-ended questions for exploratory analysis: 1) What positive or negative changes have you noticed since you started taking the medication? 2) What else would you like us to know? For adults with cognitive impairment, guardian/LAR may provide proxy answers for the surveys at the discretion of the study chair and co-chair on a case-by-case basis.

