8.2.3 Assessment of Clinical Benefit

A set of clinical benefit assessments will supplement the radiographic and the PROMIS measures. The clinical benefit assessment tools will be determined at initial screening evaluation for the subject. The same clinical benefit assessment tools will be completed at enrollment and then every 6 cycles for the duration of the study. The investigator will determine the clinical benefit assessment and have this reviewed by the study PI if no radiologic assessment is noted. See [Appendix X](#).

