8.3.3 Duration of Response

Duration of Overall Response: The overall response (substantial or intermediate) duration is measured from the time of primary endpoint measurement (6 cycles) until the first date that recurrent or progressive disease is objectively documented (taking as reference for progressive disease the smallest measurements recorded since the treatment started).

Duration of Stable Disease: Stable disease is measured from the start of the treatment until the worsening disease criteria are met, or patient on evaluation has a substantial or intermediate response.

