9.3 Statistical Analyses Plan

For all the analyses, subjects who received any dose of trametinib will be included in the analyses. The primary efficacy endpoint is objective response (including both response and partial response) at the end of cycle 6 and the primary safety endpoint is toxicity of trametinib. We will use binomial distributions to estimate the response and the toxicity rates with their 95% exact CIs. For the second primary efficacy endpoint of responses at the end of cycles 12 and 24, the response rate will also be calculated with 95% CI. For the secondary endpoint of duration of response, time from initial response to disease progression will be examined, and subjects will be censored at the last adequate disease assessment if no progression occurred by that time. We will use the log-rank tests and/or Cox proportional hazard regression to analyze the endpoint. Should the data suggest the violation of the

proportional hazard assumption, we will consider an alternative method such as accelerated failure time model analysis.

Secondary data analyses will be performed for the secondary outcomes of longitudinal measurements of radiologic assessment, PROMIS Patient Reported Outcome measurements, and Clinical Benefit Assessments, taken at screening, and at the end of cycles 6, 12, 18, and 24. The longitudinal data will be analyzed separately at each follow-up time point and together longitudinally. The paired t-test will be used to look at changes in these measures from pre-treatment levels to the post-treatment level (follow-up at cycle 3) to evaluate the treatment's short-term effects. Mixed effects models will be used for longitudinal analysis to evaluate changes in these measures over time. Should the data suggest the distributions of the measurements deviate from normal distributions, we will consider nonparametric alternatives such as Wilcoxon signed rank test or transformation. Relationships between PROMIS measures and other variables such as pain will be investigated using correlation analysis. Lastly, exploratory analyses will be performed for biomarker measures such as cell-free DNA. Descriptive statistics will be generated to summarize data.

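### Section 9.3 plans a paired test at cycle 3, where no efficacy measure is scheduled, and duration of response has different start points in 8.3.3 and 9.3

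*Protocol*

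**What the plan says.** **Timing of the measures.** Section 9.3 describes the longitudinal radiologic, PROMIS and CBA data as "taken at screening, and at the end of cycles 6, 12, 18, and 24". In the same paragraph it prescribes a paired t-test on these measures, from "pre-treatment levels to the post-treatment level (follow-up at cycle 3", to show short-term effect.

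The schedule elsewhere in the protocol is:
- PROMIS (8.2.2): "This survey battery will be administered every 6 cycles, starting at enrollment".
- CBA (8.2.3): the same tools are "completed at enrollment and then every 6 cycles for the duration of the study".
- Both (Experimental Design Schema): assessments begin at screening and "will occur at the end of every 6 cycles throughout the duration of the study and extension period".
- MRI/MRL (8.2.1.1): screening and the end of cycles 6, 12 and 24.

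**Duration of response.** Section 8.3.3 runs the duration of a substantial or intermediate response from the cycle-6 primary endpoint measurement to the first objectively documented recurrence or progression, "taking as reference for progressive disease the smallest measurements recorded since the treatment started". Section 9.3 says that "time from initial response to disease progression will be examined", with censoring at the last adequate disease assessment, and continues: "We will use the log-rank tests and/or Cox proportional hazard regression to analyze the endpoint". Section 4.1 describes a single-arm study.

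**The concern.** A paired test needs a baseline value and a cycle-3 value from the same subject. If no cycle-3 value is scheduled, the planned analysis either has no data or rests on whoever happened to be assessed early. The protocol calls for early assessment on signs of worsening, so that group would not represent the treated population.

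Duration of response is a named secondary objective (3.3). With two start points, the same subject can have two durations, and the choice could be made after the data are seen in an open-label trial where the local investigator judges response.

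**Working it through.** **1. Is there a cycle-3 efficacy assessment?**

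| Measure | Scheduled on-treatment times in the text | Cycle 3? |
|---|---|---|
| PROMIS | every 6 cycles (8.2.2, Schema, Synopsis) | no |
| CBA | every 6 cycles (8.2.3, Schema, Synopsis) | no |
| Imaging | end of cycles 6, 12, 24 (8.2.1.1, Schema, Synopsis) | no |
| Imaging, footnote to Table 8-1 | every 6 cycles | no |
| All three, section 9.3 | end of cycles 6, 12, 18, 24 | no |

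The scheduled cycle-3 assessments that the text names are the echocardiogram and ECG (6.1), which are safety measures. Efficacy values before cycle 6 can arise in two ways: an earlier assessment on signs of worsening, or extra imaging at the treating team's discretion. So the text provides no scheduled baseline-to-cycle-3 pairs.

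**2. Do the two duration definitions agree?**

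A cycle is 28 days, or 4 weeks. Let *r* be the cycle at which response is first documented and *p* the cycle at which progression is documented.
- Section 8.3.3: duration = (*p* − 6) × 4 weeks
- Section 9.3: duration = (*p* − *r*) × 4 weeks
- Difference: (*r* − 6) × 4 weeks

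| First response | Progression | 8.3.3 | 9.3 |
|---|---|---|---|
| cycle 6 | cycle 18 | (18 − 6) × 4 = 48 weeks | (18 − 6) × 4 = 48 weeks |
| cycle 12 | cycle 18 | (18 − 6) × 4 = 48 weeks | (18 − 12) × 4 = 24 weeks |
| cycle 18 | cycle 24 | (24 − 6) × 4 = 72 weeks | (24 − 18) × 4 = 24 weeks |

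For later responders, 8.3.3 counts time before the response existed.

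Section 8.3.3 itself foresees later responders, because it ends the duration of stable disease when a subject goes on to a substantial or intermediate response. A subject who is stable at cycle 6 and first responds at cycle 12 has stable disease from treatment start to week 12 × 4 = 48. The response clock, read literally, starts at week 6 × 4 = 24. The 48 − 24 = 24 weeks between are then counted both as stable disease and as response.

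**3. Which reference is used for worsening?**

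Section 8.3.3 uses the smallest on-treatment value for progression. Section 8.3.1 uses the baseline sum of longest diameters for lesion response. Section 8.3.2 mentions screening only for stable disease and gives no reference for worsening.

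As an illustration, take sums of 100 mm at screening, 60 mm at cycle 6 and 75 mm at cycle 12. The cycle-12 value is 75/60 − 1 = +25% from the smallest value and 75/100 − 1 = −25% from screening. Against the 20% threshold in 8.3.2, the classification depends on which reference is meant.

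**The case against.** **Cycle 3.** Section 9.3 also says the data will be analysed separately at each follow-up time point, so a cycle-6 comparison is already covered and little is lost. That is fair as to the size of the effect. The contradiction within 9.3 still stands. The body of Table 8-1 is not in the text reviewed, but its footnote and all the prose agree on 6-cycle intervals for these measures.

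**Start of the clock.** Cycle 6 is the first scheduled efficacy assessment, so the definitions agree for everyone who first responds there. This limits the point to later responders and to any response first seen at an unscheduled earlier visit. Section 8.3.3 might be meant for cycle-6 responders only, but then the two sections would analyse different groups of subjects, which also needs settling.

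**Log-rank and Cox.** A reader might infer that these cannot be run without a control arm. The protocol does not support that. Either can be run within one arm on baseline factors such as genotype, and those factors may be named in an SAP that is not shown. What remains is that 9.3 fixes a comparative method without naming a comparison, and names no estimate of duration itself.

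**Reference measurement.** A reader might infer that 8.3.2 and 8.3.3 contradict each other, so that one subject is both a responder and a progressor. That goes too far. Baseline for response and smallest value for progression is a coherent pairing. Section 8.3.2 also bars any response when a measure has worsened, so if worsening is read as in 8.3.3, the subject in the illustration is not a cycle-12 responder. The defect is an ambiguity.

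**Late dating of progression.** A reader might also infer that 24-week gaps date progression about 12 weeks late on average. That ignores the earlier assessment required on signs of worsening, and it is not an error in the plan.

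**Conclusion.** Two defects are established on the protocol's own wording. The paired test in 9.3 is set at a time point with no scheduled imaging, PROMIS or CBA data. Duration of response has two start points, which differ by (*r* − 6) × 4 weeks: nothing for a first response at cycle 6, 24 weeks at cycle 12 and 48 weeks at cycle 18. How many subjects this affects depends on how many first respond after cycle 6, and the protocol gives no figure for that.

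Three lesser points need clarifying: the reference for worsening in 8.3.2, the unnamed comparison for log-rank/Cox, and cycle-18 imaging. The last is included by 9.3 and the Table 8-1 footnote but omitted by 8.2.1.1, the Synopsis and the Schema.

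All of this concerns secondary analyses. The primary response rate at cycle 6 and its decision rule do not depend on the paired test or on the start of the duration clock. The conclusion on cycle 3 assumes that the body of Table 8-1 agrees with its footnote and the prose.

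**What to change.** 1. In 9.3, replace the cycle-3 time point of the paired test with the end of cycle 6, the first scheduled assessment. If an earlier effect is really wanted, a scheduled cycle-3 efficacy assessment for all subjects would be needed, at the cost of extra data collection.
2. Use one definition of duration of response in 8.3.3 and 9.3: from the first visit at which a substantial or intermediate response is documented to the first documented worsening.
3. State in 8.3.2 whether worsening is judged against screening or against the smallest on-treatment measurement, and make 8.3.3 consistent with it.
4. Estimate duration by Kaplan-Meier with a 95% CI. Keep log-rank or Cox only for named baseline factors.
5. Reconcile cycle-18 imaging across 8.2.1.1, the Synopsis, the Schema, the Table 8-1 footnote and 9.3.

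Items 1 to 4, with the paired test moved to cycle 6, are changes of wording and need no new data. Item 5 is also wording, although the choice settles whether a cycle-18 scan is required. The definitions should be fixed before responses are reviewed.

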10 DOSE MODIFICATION AND MANAGEMENT OF ADVERSE EVENTS

10.1 Dose Modifications

10.1.1 Dose Escalation

Patients with critical illness may be initiated at starting dose of 0.0125 mg/kg with approval of study chair or co-chair. If in the opinion of the site investigator this dose is tolerated may then increase to the standard 0.025 mg/kg dosing. This should take place no later than after 3 cycles of treatment.

0.032 mg/kg dosing: Prior Oncologic dosing in patients less than 6 years of age has demonstrated tolerability in those populations at 0.032 mg/kg dosing. Escalation to 0.032 mg/kg dosing prior to completion of 6 cycles of treatment only after approval of study chair or co-chair.

10.1.2 Dose Interruptions

Dose interruption because of safety and/or other medically relevant reason may last up to 60 days, afterward the subject may restart study therapy. If a patient is off therapy for up to 60 days, the study chair needs to be notified.

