10.2.1.1 Non-Hematological Dose-Modifying Toxicity

- See [Section 10.2.6](#) for management guidelines for toxicities of special interest. Note that dose modification or discontinuation of trametinib for toxicity is considered a dose modifying toxicity.
- Any Grade 4 non-hematological toxicity with specific exclusion of:
 - Grade 4 fever/pyrexia that resolves to Grade < 2 within 72 hours with supportive care (anti-pyretics)
- Dose-modifying hypertension will be considered as the following:
 - Grade 4 hypertension,
 - A blood pressure > 25 mm Hg above the 95th percentile for age, height, and gender, confirmed by repeated measurement

Note: if elevated, take 3 serial blood pressure readings from the same extremity with the patient in the same position, separated by at least 5 minutes. Avoid using the lower extremity if possible. Use the mean average of the 3 measurements.

- Any Grade 3 non-hematological toxicity with the specific exception of:
 - Grade 3 nausea and vomiting of less < 3 days duration

- Grade 3 fever or infection < 7 days duration.
- Grade 3 hypophosphatemia, hypokalemia, hypocalcemia and/or hypomagnesemia responsive to oral supplementation within 7 days
- Grade 2 allergic reactions that necessitate discontinuation of study drug will not be considered a dose-modifying toxicity
- Any Grade 2 non-hematological toxicity that persists for ≥ 7 days and is considered sufficiently medically significant or sufficiently intolerable by patients that it requires treatment interruption
- Grade 2 left ventricular ejection fraction disease
- Grade 2 cardiac valvular toxicity (mitral/aortic/tricuspid)
- Grade 2 pneumonitis
- Treatment interruption longer than 14 days due to delayed recovery from toxicity will be cause for dose modification

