10.2.3 Dose Modifications for Non-Hematologic Toxicity

If a subject experiences a dose-modifying non-hematologic toxicity as defined in [Section 10.2.1](#), the treatment will be held.

If the toxicity does not resolve to meet inclusion/exclusion parameters or baseline within 14 days of drug discontinuation the subject must be removed from protocol therapy unless specifically documented in toxicities of special interest [Section 10.2.6](#).

If the toxicity resolves to meet inclusion/exclusion parameters or baseline within 14 days of drug discontinuation the subject may resume treatment with a reduction to the next lower dose according to [Appendix II](#). See [Appendix II](#) for dosing modification in subjects receiving oral solution or the specified dose reduction in subjects receiving tablets.

- Doses reduced for toxicity will not be re-escalated, even if there is minimal or no toxicity with the reduced dose, unless otherwise specified in the toxicities of special interest [Section 10.2.6](#).
- If the same dose-modifying toxicity recurs in a subject who has resumed treatment, the subject must be removed from protocol therapy.

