Grade 2	Initiate prophylactic and reactive/symptomatic treatment measures Reassess after 2 weeks.	Dose reduction: dose reduce to the next lower dose as per Appendix II . Reassess after 2 weeks: 
 • If rash recovers to \leq grade 1 or

		baseline within 2 weeks, increase dose to previous dose level 
 If no recovery to \leq grade 1 or baseline within 2 weeks, interrupt treatment until recovery to grade \leq 1 or baseline, restart with dose reduction to the next lower dose according to Appendix II.
Grade ≥ 3	Escalate reactive/supportive treatment measures to include use of moderate strength topical steroids (Consider a brief period of oral high dose steroid such as methylprednisolone) Consult dermatologist	
 Interrupt treatment until rash recovers to grade ≤ 1 or baseline Restart treatment, dose reduction to the next lower dose according to Appendix II. If no recovery to grade ≤ 2 within 4 weeks, discontinue treatment
Other	If recurrent subjectively intolerable toxicity with at least a week interruption on 2 occasions that is not controlled by optimal supportive medications.	
 Interrupt treatment until rash recovers to grade ≤ 1 or baseline Restart treatment, dose reduction to the next lower dose according to Appendix II. If toxicity remains intolerable discontinue treatment.

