 - If the BP returns to \leq ULN within 14 days, continue trametinib at the same dose and continue anti-hypertensive therapy.
 - If the BP remains elevated ≥ 25 mmHg above the ULN or > 35 mmHg above baseline for more than 14 days after the institution/adjustment of anti-hypertensive therapy, hold trametinib, monitor BP at least every 3 days, and follow Arm 4 of the algorithm from the point that trametinib is held. The anti-hypertensive therapy should be continued until the BP is less than the ULN.
- If the BP returns to \leq ULN within 14 days, restart trametinib at reduced dose (See [Appendix II](#)).
- If the BP remains $>$ ULN for more than 14 days, subject must be removed from protocol therapy.
 - If the BP increases to > 25 mm Hg above the ULN despite anti-hypertensive therapy, hold trametinib, but continue the anti-hypertensive agent(s). Monitor the BP as clinically indicated and follow Arm 4 of the algorithm from the point that trametinib is held.

Arm 4 of algorithm:

- If BP is > 25 mm Hg above the ULN hold trametinib, monitor BP, and administer/adjust antihypertensive therapy as clinically indicated.
 - If the BP returns to \leq ULN within 14 days, trametinib may be restarted at a reduced dose.
 - If the BP is $>$ ULN for > 14 days, the subject must be removed from protocol therapy

Arm 5 of algorithm:

- If the subject develops Grade 4 hypertension, discontinue trametinib, monitor BP and administer anti-hypertensive therapy as clinically indicated. The subject is Off Protocol Therapy.

10.2.6.12 *Treatment Dose Modifications and Guidelines for Paronychia*

Management of Paronychia:

Systemic antibiotics can be used for initial treatment of paronychia. For recurrent paronychia, or paronychia involving other additional digits flurandrenolide (e.g. Cordran) tape or a topical steroid cream such as triamcinolone can be used in the morning and mupirocin and ketoconazole topical ointments in the evening. If no improvement is seen, a dermatology or surgery consultation is recommended. For infected lesions, bacterial and fungal culturing followed by the appropriate culture-driven systemic or topical antibiotics is indicated. Rarely, surgical removal of the nail may be necessary as clinically indicated.

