10.4 Criteria for Removal from Protocol Therapy and Off Study Criteria

10.4.1 Criteria for Removal from Protocol Therapy

- a) Intolerable toxicity (leading to treatment interruption >4 weeks)
- b) Worsening disease at any time at the discretion of the investigator
- c) Refusal or withdraw of consent for further protocol therapy by parent/guardian/LAR or subject
- d) Physician determines it is in subject's best interest
- e) Completion of planned therapy
- f) Non-compliance with protocol requirements (e.g., unexcused missing more than one scheduled study visit or missing > 15% of doses of study drug)

Subjects who are off protocol therapy are to be followed (as indicated) until they meet the criteria for Off Study (see below). For subjects who withdrawal due to AE, the medical condition will be tracked for at least a month after discontinuing the study drug or until resolution of the AE.

Follow-up data will be required until one of the following off study criteria is met.

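### For non-hematologic toxicity outside Section 10.2.6, a hold longer than 14 days leads to removal, dose modification or permitted restart depending on the section read, and no rule takes precedence

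*Protocol*

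**What the plan says.** Four sections of the protocol deal with a prolonged hold.

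- **Section 10.1.2, Dose Interruptions.** The scope is "Dose interruption because of safety and/or other medically relevant reason". Such an interruption "may last up to 60 days, afterward the subject may restart study therapy". The only further step is to notify the study chair.
- **Section 10.2.3, Dose Modifications for Non-Hematologic Toxicity.** Drug is held for a dose-modifying toxicity. If the toxicity has not returned to baseline or to the eligibility limits, the rule reads "within 14 days of drug discontinuation the subject must be removed from protocol therapy unless specifically documented in toxicities of special interest". If it resolves in that time, the subject may resume at the next lower dose.
- **Section 10.2.1.1, Non-Hematological Dose-Modifying Toxicity.** "Treatment interruption longer than 14 days due to delayed recovery from toxicity will be cause for dose modification".
- **Section 10.4.1(a), Criteria for Removal from Protocol Therapy.** "Intolerable toxicity (leading to treatment interruption >4 weeks" is a removal criterion.

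Section 10.2.6 sets separate limits for events of special interest. For example, hypertension above the upper limit "for more than 14 days, subject must be removed from protocol therapy", and Grade 3 or higher rash without sufficient recovery "within 4 weeks, discontinue treatment". Section 10.2.4 governs hematologic toxicity and sets no 14-day removal limit.

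**The concern.** Section 10.1.2 expressly includes safety interruptions, so it covers toxicity holds. It does not defer to 10.2.3, 10.2.1.1 or 10.4.1. Section 10.2.3 defers only to 10.2.6. A site that follows the text literally can therefore find one section that removes a subject and another that lets the same subject restart.

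The first stake is safety: whether a subject is re-exposed after a toxicity that was slow to resolve should not depend on the section a site happens to consult. The second is interpretation. Safety is a co-primary objective, and discontinuations for toxicity feed the tolerability result. With 25 sites and 39 evaluable subjects, a few divergent decisions would change who is still on treatment when response is assessed at the end of cycle 6.

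**Working it through.** The protocol gives no figure to reproduce, so the check sets the rules side by side and counts days.

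**Inputs**
- 10.1.2: restart allowed after an interruption of up to 60 days, safety included.
- 10.2.3: removal if not resolved within 14 days, outside 10.2.6.
- 10.2.1.1: dose modification if the interruption exceeds 14 days because of delayed recovery.
- 10.4.1(a): removal if intolerable toxicity leads to an interruption of more than 4 weeks (4 × 7 = 28 days).
- Cycle length: 28 days.

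**Assumption.** The hold starts when the drug is stopped and ends when the toxicity resolves, so time to resolution equals length of interruption.

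**Two worked cases** for a non-hematologic dose-modifying toxicity outside 10.2.6:

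| Rule | Resolves on day 20 | Resolves on day 35 |
|---|---|---|
| 10.2.3 | Removed (20 > 14) | Removed (35 > 14) |
| 10.2.1.1 | Dose modified (20 > 14) | Dose modified (35 > 14) |
| 10.4.1(a) | Not reached (20 < 28) | Removed if judged intolerable (35 > 28) |
| 10.1.2 | May restart (20 ≤ 60) | May restart (35 ≤ 60) |

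**Conflict windows**
- 10.1.2 against 10.2.3: days 15 to 60, which is 60 − 14 = 46 days.
- 10.1.2 against 10.4.1(a): days 29 to 60, which is 60 − 28 = 32 days.
- 10.2.1.1 against 10.2.3: from day 15. Dose modification presupposes that treatment continues; removal ends it.

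**Scale against the primary assessment.** Six cycles are 6 × 28 = 168 days.
- 14/168 = 8.3%
- 28/168 = 16.7%
- 60/168 = 35.7%

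These are shares of the time to the cycle 6 assessment. They are not effects on the response rate or the toxicity rate.

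**Does anything rank the rules?** Section 10.2.3 gives way to 10.2.6 and to nothing else. Section 10.1.2 contains no cross-reference. Section 10.4.1 does not mention 10.1.2. The general schedule in Section 10.10 adds an instruction for Grade 3 events to interrupt until Grade 0-1 and resume at a lower level, with no time limit, so it does not settle the matter.

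**The case against.** The strongest reply is that these are not rival values of one parameter. Section 10.1.2 caps any interruption, 10.2.3 limits time to recovery from a defined class of toxicity, and 10.4.1(a) applies to intolerable toxicity. A general ceiling with stricter specific rules beneath it is a common structure, and restart under 10.1.2 is permitted, not required. The 14-day bullet in 10.2.1.1 stands in a list of definitions. It can be read as applying where 10.2.6 allows recovery beyond 14 days.

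Part of this stands. Section 10.1.2 raises no difficulty for interruptions unrelated to toxicity, and the limits in 10.2.6 are stated exceptions to 10.2.3: 7 days for diarrhea, 14 days for hypertension, and 4 weeks for Grade 3 or higher rash, asymptomatic LVEF decrease, pneumonitis, and Grade 3-4 retinal pigment epithelial detachment. It does not remove the conflict. Section 10.1.2 names safety in its own scope. Sections 10.1.2 and 10.4.1(a) are both general, so specificity cannot rank 60 days against 4 weeks. Nothing in 10.2.1.1 confines its bullet to the events in 10.2.6.

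Three stronger readings are tempting, and the protocol does not support them.

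- **That any toxicity hold of 20 days requires removal under 10.2.3.** It does not: 10.2.3 yields to 10.2.6, and hematologic toxicity falls under 10.2.4.
- **That a 28-day hold also breaches the limit of 15% missed doses in 10.4.1(f).** That item concerns non-compliance, which a protocol-directed hold is not, and it states no denominator.
- **That removal decides who is evaluable for response.** Section 8.3.1 asks for one cycle of therapy and a disease re-evaluation, with earlier progression also counted, and Section 9.3 includes everyone who received any dose. Neither requires being on drug at cycle 6.

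**Conclusion.** The inconsistency is real but bounded. It covers days 15 to 60 of a hold for non-hematologic dose-modifying toxicity outside Section 10.2.6, and days 29 to 60 for intolerable toxicity under 10.4.1(a). Within those windows the text supports opposite actions for the same subject and states no precedence.

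The consequences are for safety, for discontinuation and tolerability results, and for on-treatment status at cycle 6. The sample size, power and type I error figures are unaffected. The protocol gives no basis for estimating how many subjects would have such a hold, so no effect on the response rate is claimed. The day counts rest on the assumption that resolution and restart coincide; if restart comes later than resolution, the two clocks differ and the windows shift. This should be corrected because the text is wrong as it stands, whichever limit is intended.

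**What to change.** Reconcile Sections 10.1.2, 10.2.1.1, 10.2.3 and 10.4.1(a) in one amendment:

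1. State whether 10.1.2 applies to toxicity holds or only to other medical interruptions.
2. State which rule takes precedence when more than one applies.
3. Give a single consequence for a non-hematologic dose-modifying toxicity that takes more than 14 days to resolve, so that 10.2.1.1 and 10.2.3 agree.
4. Cross-reference the existing exceptions in 10.2.6 and the hematologic rule in 10.2.4.

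The clinical team sets the limits; nothing here favors one of them. The cost is amendment wording and notice to sites. The design, sample size and analysis do not change.
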